7.4 Re-Enrolment

Re-enrolment of Subjects is only allowed for subjects who failed screening or have to stop the study participation before randomization. After 4 weeks waiting time re-enrolment will be allowed once. However, Subjects who were withdrawn at visit V2 due to an exacerbation (moderate and/or severe exacerbation, and/or treated with antibiotics) between visits V0 and V2 may be re-enrolled after resolution of the exacerbation. If, during the second enrolment, the Subject again experiences such an exacerbation, the Subject must be withdrawn and no further re-enrolment is allowed.

In case a Subject is re-enrolled, the exclusion criteria nos. 1 and 28 do not apply. (see Section 7.2).

After having been randomized the Subject cannot be re-enrolled. For re-enrolled Subjects a new CRF has to be filled in starting at visit V0. A comment specifying that the Subject has been re-enrolled must be given on the screening log and in both CRFs.

7.5 Diet, Fluid, Activity Control

Subjects should not take any food or drink overnight for at least 8 hours prior to returning to the study center for all visits. Subjects will also be asked to avoid strenuous exercise for 8 hours prior to each study visit and to avoid smoking for 4 hours prior to each study visit. For visits where subjects will not undergo blood draws or biopsies, the fasting requirement will only be mandated if clinically indicated as per investigator judgment.

Study medication will be administered once daily in the morning after breakfast with water. On study visit days where the subject is required to fast, study medication will be taken with water only.

7.6 Excluded Medications

The following medications are not allowed throughout the trial and are to be withdrawn prior to or at V0:

1. Inhaled Corticoid Steroids (ICS) or intranasal corticosteroids.
2. Combined formulas of inhaled Long-Acting β_2 -Agonists (LABA) and ICS (LABA/ICS).
3. Theophylline and/or derivatives (aminophylline, diprophylline) or combinations thereof or any other theophylline containing products.
4. Oral β_2 -agonists.
5. Lipoxygenase inhibitors.
6. Leukotriene antagonists.
7. Any combinations of the above mentioned medications.
8. Oral or parenteral anticoagulant therapy: heparin or low molecular weight heparin (LMWH), vitamin K antagonists (e.g. warfarin); factor Xa (e.g. fondaparinux) or thrombin inhibitors (e.g. argatroban).
9. Antiplatelet therapy with thienopyridine (e.g. ticlopidine, clopidogrel, prasugrel) or non-thienopyridine drugs (e.g. cangrelor, ticagrelor).
10. Oral/parenteral glucocorticosteroids or any other immunosuppressive medication (e.g. cyclosporine, methotrexate, TNF alpha receptor inhibitors or antibodies, gold, azathioprine).
11. All available phosphodiesterase 4 (PDE4) inhibitors.

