7.2 Exclusion Criteria

Subjects meeting any of the following criteria will be excluded from trial enrolment:

Criteria affecting the read-out parameters of the trial:

1. Clinical instability, defined as experiencing a COPD exacerbation six months prior to V0, as indicated by treatment with a systemically administered glucocorticosteroid and/or antibiotics and/or hospitalization.
2. An upper/lower respiratory tract infection e.g. common cold, sinus symptoms, pneumonia, which has not resolved four weeks prior to V0.

² Total pack years = No. cigarettes smoked per day/20 x no. years of smoking. For the purpose of the trial a former smoker is defined as a subject who has not smoked for ≥ 12 months at visit V0. Smoking status will be monitored throughout the trial but not verified by any objective tests.

3. Diagnosis of asthma and/or other relevant lung disease (e.g. history of primary or clinically significant bronchiectases, cystic fibrosis, bronchiolitis, lung resection, lung cancer, interstitial lung disease [e.g. fibrosis, silicosis, sarcoidosis], active tuberculosis) or previous episodes of pneumothorax.
4. Known alpha-1-antitrypsin deficiency.

Criteria within ethical considerations in terms of general health:

5. Duration of oxygen therapy ≥ 12 h/day.
(**GERMANY ONLY:** Any oxygen therapy at home.)
6. History of intubation for COPD or a respiratory failure of any cause in the past year.
7. Hypoxemia defined as oxyhemoglobin concentration $< 88\%$ when breathing room air measured by pulse oximetry.
8. Formal contraindications to sputum collection or impossibility to obtain a sample of sputum valid for analysis.
9. Clinically relevant abnormal laboratory values suggesting an undiagnosed disease requiring further clinical evaluation (as assessed by the Investigator).
10. Suspicion or diagnosis of a bleeding disorders irrespective of its pathophysiological mechanism: Thrombocytopenia (platelets $< 50000/\text{mL}$) and platelet dysfunction (e.g. uraemia), thrombotic or coagulation disorders and bleeding due to abnormal blood vessels (e.g. purpura simplex).
11. Severe psychiatric or neurological disorders.
12. History of depression associated with suicidal ideation or behaviour.
13. Hemodynamic instability (e.g. bradycardia with resting heart rate < 60 beats per min, tachycardia with resting heart rate ≥ 120 beats per min and/or a systolic blood pressure < 100 or > 180 mmHg).

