25. Female Subjects of childbearing potential, not using or not willing to continue using a medically reliable method of contraception for the entire trial duration, such as oral, injectable, or implantable contraceptives, or intrauterine contraceptive devices, unless they are surgically sterilized/hysterectomized or post-menopausal >1 year or who are not using any other method of contraception considered sufficiently reliable by the Investigator in individual cases.
26. Pregnancy, breast feeding, planned oocyte donation or oocyte implantation
27. Planned donation of germ cells, blood, organs or bone marrow during the course of the trial.
28. Participation in another clinical trial (use of investigational product or device) within 30 days preceding the baseline visit V0 or re-entry of Subjects previously enrolled in this trial (for exemption see Section 7.4).

29. Suspected inability to comply with trial procedures (e.g. repeated bronchoscopies, bronchial biopsy and sputum induction procedures, language problems, psychological disorders).
30. Suffering from any concomitant disease that might interfere with trial procedures or evaluations according to the Investigator's judgement.
31. Use of disallowed drugs.
32. Employee at the investigational site, relative or spouse of the Investigator.

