9.3.1 Screening / Visit 0 (V0)

Subjects for whom written informed consent has been obtained (see Section [9.1.1](#)) will undergo the following assessments or procedures:

- Demographic data (e.g. race, sex, date of birth)
- Medical History and concomitant diseases (all relevant previous illnesses, which may or may not be still ongoing at V0, are to be documented)
- COPD history and history of COPD exacerbations
- Check of inclusion and exclusion criteria (see Sections [7.1](#) and [7.2](#))
- Previous and concomitant medications (see Sections [7.6](#), [7.7](#), [9.1.2](#))
- Substance use (smoking status)
- Physical examination (see Sections [9.1.3](#))
- Vital signs (e.g. heart rate, blood pressure) and body measurements (body weight and height) (see Sections [9.1.4](#), [9.1.5](#))
- Standard laboratory (including urine analysis and blood pregnancy test for females of childbearing potential, see Section [9.1.9](#))
- Clotting time and platelet count (see Section [9.1.9.2](#))
- Chest X-ray or CT-scan (if not performed within the last three months – results must be available)
 - **GERMANY ONLY:** Every patient should have a historical X-ray or CT scan available to clarify the exclusion criteria #18.
- 12-lead ECG (see Section [9.1.12](#))
- Pulmonary function test (see Section [9.1.16](#))

For Subjects who meet the inclusion criteria:

- Withdrawal of disallowed COPD medication (see Section [7.6](#))
- Dispense patient card

- The adverse event monitoring will be explained (see Section 10.2.1)
- Call IVRS and dispense trial treatment

Further procedures

The Subject will be asked to return to the investigational site for visit V1 four weeks after visit V0.

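### Section 7.6 and the Appendix A V0 row order all 11 disallowed drug groups stopped by V0, anticoagulants, antiplatelets and immunosuppressants included, while 9.3.1 limits the stop to COPD drugs and exclusion 31 does not separate wash-out from exclusion

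*Protocol*

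**What the plan says.** Four places in the protocol bear on what happens to a subject who arrives on a disallowed drug.

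- **Section 7.6.** One lead-in covers the whole list: "The following medications are not allowed throughout the trial and are to be withdrawn prior to or at V0". Items 1 to 7 are inhaled or intranasal corticosteroids, LABA/ICS combinations, theophyllines, oral beta-agonists, lipoxygenase inhibitors, leukotriene antagonists and combinations of these. Item 8 is "Oral or parenteral anticoagulant therapy". Item 9 begins "Antiplatelet therapy with thienopyridine" and goes on to non-thienopyridine agents. Item 10 is "Oral/parenteral glucocorticosteroids or any other immunosuppressive medication". Item 11 is other PDE4 inhibitors.
- **Appendix A.** A row marked at V0 calls for disallowed medications to be withdrawn. It is not limited to COPD drugs.
- **Section 9.3.1.** The visit instruction for V0 is narrower: "Withdrawal of disallowed COPD medication", with a cross-reference to 7.6. It stands in a block headed "For Subjects who meet the inclusion criteria". The check of inclusion and exclusion criteria comes earlier in the same section.
- **Section 7.2.** The lead-in is "Subjects meeting any of the following criteria will be excluded from trial enrolment", and criterion 31 reads "Use of disallowed drugs".

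**The concern.** Items 1-7 and 11 are mostly respiratory drugs that have to be cleared before airway inflammation is measured. Items 8 to 10 are different. Anticoagulants and antiplatelets are normally given to protect against another disease, and immunosuppressants often are. For a subject who needs such a drug, the safe rule in a biopsy trial is not to enrol the subject. Section 7.6 gives both kinds of drug the same order, to withdraw, and sets no condition about clinical need. The ban lasts for the whole trial (up to 24 weeks by section 6.1), so it is not a short pause around each bronchoscopy.

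Two things are at stake. One is safety: a site following 7.6 or the Appendix A row as written could stop a drug prescribed for another disease so that the subject can enter. The other is uneven eligibility, because one site may exclude a user of an item 8 drug where another washes the drug out.

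**Working it through.** No formula applies. The check sets the texts side by side.

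**1. Scope of each instruction**

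| Place | Drugs covered | Action |
|---|---|---|
| 7.6 lead-in | all 11 items | withdraw before or at V0 |
| Appendix A, V0 row | disallowed drugs, no limit | withdraw |
| 9.3.1, V0 step | disallowed COPD drugs, pointing to 7.6 | withdraw |
| 7.2, no. 31 | disallowed drugs, no limit | exclude |

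The scope of withdrawal differs between 9.3.1 and the other two places. For the same unrestricted set of drugs, 7.6 says withdraw and 7.2 says exclude.

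**2. Count of items.** Items 8, 9 and 10 are 3 of 11. Items 1-7 and 11 are 7 + 1 = 8 of 11. Together 3 + 8 = 11.

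**3. Does exclusion 31 settle the matter alone?** Suppose it bars everyone who is using a 7.6 drug on arrival at V0. The 9.3.1 stop step would then apply to nobody. Yet inhaled-steroid users are plainly meant to be stopped and enrolled: section 13.1.3.2 uses former ICS use as a subgroup and model factor, and Appendix K (1.4) says that steroids are withdrawn in the run-in. So exclusion 31 must allow entry after a stop for at least some items, and its wording does not say which. Section 7.6 also allows withdrawal before V0. A subject taken off an item 9 drug shortly before V0 is no longer a user at V0 and would pass exclusion 31 as worded. The recheck of admission criteria at V2 (section 7.3) does not help, since that subject would pass there too.

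**4. Can the texts be reconciled?** Largely. Take 9.3.1 as the specific rule: COPD drugs are stopped, and use of any other disallowed drug remains an exclusion under no. 31. This is probably what is meant. It requires a site to disregard the breadth of the 7.6 lead-in and of the Appendix A row.

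**5. Who is left?** These criteria narrow the group:
- no. 1: an exacerbation in the six months before V0, with systemic steroids among its markers (section 7.4 waives this for re-enrolled subjects);
- no. 10: thrombotic and coagulation disorders;
- no. 16: significant arrhythmias or valve deformations;
- no. 17: angina of class II or above, or infarction within 12 months;
- no. 19: immunological diseases;
- no. 30: investigator judgement on concomitant disease.

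Aspirin at 75-325 mg stays permitted under 7.7. The group need not be empty. Exclusion 17 admits subjects whose coronary disease was revascularised at least 3 months before V0 and who have had no symptoms since, and exclusion 16 covers only haemodynamically significant arrhythmias. That some of these subjects take an item 8 or 9 drug is a clinical assumption. The protocol gives no figure.

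**The case against.** A reader might infer from 7.6 that nothing in the protocol excludes users of items 8 to 10. The documents do not support that. Exclusion 31 applies under the section 7.2 lead-in, sits among the criteria grouped under ethical and general-health considerations, and is checked at V0 in a list that precedes the stop step. Sections 7.0 and 9.1.14 also require entry criteria to be confirmed before randomization. With 9.3.1 naming only COPD medication, the better reading is that these users are kept out.

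It can be added that the Appendix A row is only a short table label and that harm would need a site to pass over exclusion 31, 9.3.1, several diagnosis criteria and its own judgement. Barring these drugs before endobronchial biopsy is itself protective. All of this stands, and it limits the weight of the point. It does not remove the conflict: 7.6 is the section that 9.3.1 sends the site to, its instruction is explicit, and exclusion 31 treats all 11 items alike although some are clearly meant to be washed out.

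A second fair objection concerns item 10. It contains oral glucocorticosteroids, which can be COPD treatment, and Appendix K does not limit its steroid withdrawal to inhaled products. Making all of item 10 exclusion-only would decide an eligibility question that belongs to the sponsor. This is accepted, and the fix below leaves that question open.

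**Conclusion.** The conflict is real, and correcting it is a cheap improvement. Section 7.6 and the Appendix A row order withdrawal of all 11 groups, 9.3.1 orders it for COPD drugs only, and exclusion 31 does not separate wash-out groups from exclusion groups. For 3 of the 11 items the plain words of 7.6 tell a site to stop a drug, with no clinical-need condition, where the rest of the protocol points to exclusion.

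The affected group is likely to be small, given the criteria that narrow it. The protocol gives no number, and no size of harm is claimed. The conclusion rests on the wording alone, plus the clinical assumption that some otherwise eligible subjects take an item 8, 9 or 10 drug for another disease. A reader might also infer a threat to the primary result. There is no basis for that: the CD8+ comparison and its error rate do not depend on how this is resolved.

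**What to change.** - In 7.6 and the Appendix A row, limit withdrawal before or at V0 to items 1-7 and 11. All 11 groups stay prohibited during the trial.
- In the 9.3.1 stop step, cite items 1-7 and 11 in place of the phrase about COPD medication. Item 1 includes intranasal corticosteroids, which that phrase does not clearly cover.
- In 7.6 and exclusion 31, state that subjects who need an item 8 or 9 drug, or an item 10 drug for a disease other than COPD, are not eligible, and that these drugs must not be stopped for the purpose of enrolment.
- The sponsor should state separately whether oral glucocorticosteroids taken for COPD may be washed out.

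The cost is a wording amendment in four places (exclusion 31, 7.6, one line of 9.3.1 and one Appendix A row) with no new procedures. The downside is possibly a few fewer eligible subjects.

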7.7 Allowed Concomitant Medications

1. Rescue medication (any SABA or SAMA) can be used as rescue medication according to the individual needs of a Subject.
2. *Prn* NSAIDs
3. Use of acetylsalicylic acid in doses 75-325 mg for primary or secondary cardiovascular prophylaxis
4. Prophylactic vaccination is allowed throughout the trial
5. Other drugs for the treatment of concurrent diseases are allowed. However, their dosages should be kept constant throughout the trial.

Limited concomitant medication:

1. Therapy consisting of any bronchodilator such as SABA, SAMA, LABA, LAMA starting at least six weeks prior to V0 is allowed. The treatment must remain stable in the course of the whole trial six weeks of single-blind placebo administration (run-in) and 16 weeks of double-blind treatment period.

7.8 Criteria for Discontinuation or Withdrawal of a Subject

The primary reason for discontinuation or withdrawal of the subject from the study or study medication should be recorded in the case report form (CRF) using the following categories. For screen failure subjects, refer to Section 9.1.13.

- Adverse event (AE). The subject has experienced an AE that requires early termination because continued participation imposes an unacceptable risk to the subject's health or the subject is unwilling to continue because of the AE.
- Continued participation in the trial appears to be medically harmful to the Subject (Investigator judgement)
- The Subject wishes to be withdrawn (withdrawal of consent)
- Lost to follow-up
- Closure of investigational site
- Pregnancy or lack of adequate contraception in women of childbearing potential

Note: If the subject is found to be pregnant, the subject must be withdrawn immediately. The procedure is described in Section 9.1.10.

- Breaking the blind
- Meeting at least one of the following discontinuation criteria:
 1. COPD exacerbation between V0 and V2 (as defined by the need for oral or parenteral glucocorticosteroid intake and/or hospitalization)
 2. A deterioration in pulmonary function that in the judgment of the Investigator compromises a Subject's health

In case of hospitalization, the Investigator should notify the Sponsor within 24 hours (see Section 10.2.2).

A Subject that has been prematurely discontinued, if possible should be called in for a last visit. All procedures listed for VE (visit end, V6) should be completed at this visit. Procedures to be followed in case of premature discontinuation in relation to the point in time during the trial are given in Section 9.3.5. Even if the Subject is not able to attend, the CRF must be completed with all available data and the Drug Accountability Form must be filled in as well. If possible, the Subject must return all trial treatment.

In case of Subjects lost to follow-up, every reasonable effort should be made to contact the Subject to encourage the Subject to continue trial participation as scheduled.

If the Subject withdraws consent, no further evaluations should be performed and no attempts should be made to collect additional data.

Subject recruitment will continue until the planned number of randomized Subjects is reached. All reasons for early withdrawal will be recorded in the CRF.

For follow-up of AEs please refer to Section [10.2.1](#).

For discontinuation criteria for the trial please refer to Section [6.3](#).

7.9 Procedures for Discontinuation or Withdrawal of a Subject

The investigator may discontinue a subject's study participation at any time during the study when the subject meets the study termination criteria described in Section [7.8](#). In addition, a subject may discontinue his or her participation without giving a reason at any time during the study. Should a subject's participation be discontinued, the primary criterion for termination must be recorded by the investigator. In addition, efforts should be made to perform all procedures scheduled for the Early Termination Visit. Discontinued or withdrawn subjects will not be replaced.

8.0 CLINICAL TRIAL MATERIAL MANAGEMENT

This section contains information regarding all medication and materials provided directly by the sponsor, and/or sourced by other means, that are required by the study protocol, including important sections describing the management of clinical trial material.

8.1 Study Medication and Materials

8.1.1 Dosage Form, Manufacturing, Packaging, and Labeling

Study medication refers to Roflumilast 500 µg tablets and matching placebo tablets. Study medication will be packaged in a blinded fashion. The terms “study medication” and “investigational drug” and “sponsor-supplied drug” may be used interchangeably.

All study medication supplied by the Sponsor for this trial will be manufactured, tested and released according to current Good Manufacturing Practice (GMP) guidelines.

The study medication for this trial will be packed and labelled according to current GMP guidelines, Good Clinical Practice (GCP) guidelines and local regulations.

8.1.1.1 Investigational drug

- Roflumilast, 500 µg tablet, once daily, oral administration in the morning after breakfast.
- Placebo tablet, once daily, oral administration in the morning after breakfast.

Roflumilast 500 µg and placebo will be supplied as yellow triangular tablets in wallet cards containing 60 tablets. Each Roflumilast tablet contains 500 µg Roflumilast. Placebo tablets will have an identical appearance.

Each medication kit may have a label with a tear-off part. When the medication is issued to the Subject, if there is a tear-off part, it must be removed and attached to the Subject’s Drug Accountability Form included in the CRF.

The investigational sites will be supplied with study medication according to the site’s needs depending on the rate of Subject enrolment. Each site will have an individual stock of study medication, which will be resupplied continuously as soon as the amount of study medication will fall below a predefined minimum level. This will be managed by an Interactive Voice Response System (IVRS)/Interactive Web Response System (IWRS).

The study medication will be dispensed at visits V0, V2, and V4. At each dispensing visit, Subjects will be supplied one (V0) or two (V2, V4) wallet cards of study medication (placebo or Roflumilast) each containing 60 tablets (see [Table 8.a](#)). Study medication dispensing at visits V2 and V4 allows for a four weeks recovery period in case the Subject experiences an exacerbation (see Section [9.3.4](#)).

Table 8.a Dispensing of Trial Treatment

Visit	No. of weeks since randomization	No. of weeks to next dispensing / returning visit	No. of wallet cards to be dispensed	Number of tablets
V0	-6	6	1	60
V1	-2	-	-	-
V2	0	6	2	120
V3	≤2	-	-	-
V4	6	10	2	120
V5	14	-	-	-
V6	16	-	-	-

8.1.2 Storage

Investigational drug must be kept in an appropriate, limited-access, secure place until it is used or returned to the sponsor or designee for destruction. Study medication must be stored below 30°C, and remain in the original container until dispensed. A daily temperature log of the drug storage area must be maintained every working day.

8.1.3 Dose and Regimen

The approved dose in the EU is Roflumilast 500 µg.

Subjects will be asked to self-administer the trial treatment according to the following regimen:

- Single-blind baseline period (V0-V2): one placebo tablet once daily.
- Double-blind treatment period (V2 [randomization]-VE): one tablet containing placebo or Roflumilast 500 µg once daily.

The tablets must be taken orally in the morning after breakfast with some water. On study visit days where the subject is required to fast, study medication will be taken with water only.

